14. STATISTICAL CONSIDERATIONS

14.1 Milestones

14.1.1 Registration Date

The date the subject signs the informed consent.

14.1.2 Enrollment (On Study) Date

The date of initiation of study treatment on Cycle 1, Day 1.

14.1.3 Treatment Discontinuation Date

The date the investigator makes the decision to discontinue elotuzumab. See Section 9 for criteria for discontinuation of treatment.

14.2 Sample Size Determination

The primary objective of this study is to evaluate the very good partial response or better (VGPR+) rate in subjects treated with elotuzumab in addition to the combination of carfilzomib, lenalidomide, and dexamethasone (KRd) in relapsed or refractory multiple myeloma subjects. This will be evaluated in terms of the percent of subjects who achieve a VGPR+ to induction therapy. Wang [6] reported a VGPR+ rate of approximately 40% in this patient population treated with KRd. See Section 1.4 for the rationale for using this as the historical control. This study will be used to test the null hypothesis that the VGPR+ rate in subjects treated with elotuzumab+KRd is less than or equal to 40%. Forty (40) response evaluable subjects will be enrolled, and if at least 21 of 40 subjects achieve a VGPR+, the null hypothesis will be rejected. The design will provide 90% power with a 1-sided alpha = 0.10 significance level, assuming the true VGPR+ rate is 60%. An improvement from 40% to 60% in the VGPR+ rate is considered clinically relevant.

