14.5.4 Primary Analysis

The frequency and proportion of subjects experiencing a VGPR+ will be calculated. A corresponding 95% confidence interval will be estimated using the Clopper-Pearson method. A one-sided test for binomial proportions using the rejection region described in the sample size section (Section 14.2) will be carried out, testing the null hypothesis that the VGPR+ rate is less than or equal to 40%. Based on the design and corresponding sample size calculations described in Section 14.2, if at least 21 subjects experience a VGPR+, the null hypothesis can be rejected.

Logistic regression techniques will be used to correlate VGRR+ rate with baseline subject and disease characteristics, and results from biomarker studies as previously described. This will include univariate and multivariable regression model techniques to identify individual and independent prognostic factors.

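### The stated 90% power is not what the 21-of-40 rule delivers: its exact power at a 60% rate is 87.0%, and no cut-off at n = 40 gives both alpha at or below 0.10 and 90% power

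*Combined protocol and SAP*

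**What the plan says.** Section 14.2 sets out the whole design. The hypothesis to be rejected is a VGPR+ rate of 40% or lower. On size and decision rule: "Forty (40) response evaluable subjects will be enrolled, and if at least 21 of 40 subjects achieve a VGPR+, the null hypothesis will be rejected". On operating characteristics: "The design will provide 90% power with a 1-sided alpha = 0.10 significance level, assuming the true VGPR+ rate is 60" per cent. The Statistical Considerations entry of the synopsis repeats these statements.

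Section 14.5.4 makes the same rule the primary test: "A one-sided test for binomial proportions using the rejection region described in the sample size section (Section 14.2) will be carried out". It restates the threshold: "if at least 21 subjects experience a VGPR+, the null hypothesis can be rejected". That section makes no power claim of its own.

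Nothing else in the plan alters the calculation. Section 14.5.7 plans no interim analysis, and Section 3.4 continues enrolment until the evaluable target is met, so 40 is the analysed number and not a figure to be reduced for dropout.

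**The concern.** Power belongs to the rule that will be applied. Here the rule is a fixed count out of a fixed number, so its power at 60% is one binomial tail probability and needs no approximation. With only 40 subjects the count is coarse: moving the cut-off by one changes both error rates by several percentage points. A nominal alpha of 0.10 and a nominal power of 90% may therefore not be attainable together, and a power figure taken from a continuous approximation may not describe the integer rule.

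At stake is the reading of a negative result. This is the only power statement in the plan, and it tells the reader that a true 60% rate would be missed one time in ten. If the actual chance is higher, the risk of discarding an active regimen is understated. A positive result is affected only if type I error exceeds 0.10, so that has to be checked too.

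**Working it through.** **Inputs** (Section 14.2; the rule is confirmed in 14.5.4)

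- Null rate p0 = 0.40; alternative p1 = 0.60
- One-sided alpha = 0.10; stated power 0.90
- n = 40; reject if X ≥ 21, where X is the number of VGPR+ responders

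**Step 1. Where 90% can be reproduced.** The plan names no power method. The usual one-sample formula for a proportion, without continuity correction, uses z = 1.2816 for both one-sided alpha 0.10 and power 0.90. The variance term is the same at both rates, because 0.4 × 0.6 = 0.6 × 0.4 = 0.24:

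- n = [(1.2816 + 1.2816) × √0.24 / 0.20]² = 39.4, rounded up to 40.
- At n = 40 the standard error is √(0.24/40) = 0.0775, and power = Φ(0.20/0.0775 − 1.2816) = 90.3%.
- The critical count implied by this test is 40 × (0.40 + 1.2816 × 0.0775) = 19.97, so it rejects at 20 responders.

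The formula reproduces both n = 40 and about 90% power, but for a cut-off of 20. Two other calculations that ignore the integer rule also land close to 90%: the arcsine approximation gives 89.7% and a randomised exact test gives 89.6%.

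**Step 2. Exact properties at n = 40.** With X ~ Binomial(40, p), type I error is P(X ≥ r | p = 0.40) and power is P(X ≥ r | p = 0.60):

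| Cut-off r | Type I error at 40% | Power at 60% |
|---|---|---|
| 20 | 0.1298 | 0.9256 |
| **21 (the plan)** | **0.0744** | **0.8702** |
| 22 | 0.0392 | 0.7911 |

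A cut-off of 21 is the smallest that keeps type I error at or below 0.10, and its power is 87.0%. A lower cut-off breaks alpha; a higher one loses more power. No integer rule at n = 40 meets both targets.

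**Step 3. Cross-check on the stated rule.** The normal approximation to P(X ≥ 21 | p = 0.60), with mean 24 and standard deviation √(40 × 0.24) = 3.098, gives 87.1% with continuity correction (using 20.5) and 83.4% without it (using 21). Neither gives 90%.

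**Step 4. Size of the gap.**

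- Power: 90% − 87.0% = 3.0 percentage points.
- Type II error: 1 − 0.870 = 13.0% against 10%. A true 60% rate would be missed about once in 7.7 trials (1/0.130), not once in 10.
- Solving P(X ≥ 21 | 40, p) = 0.90 gives p = 0.612, so the rule reaches 90% power at a true rate of 61.2%.

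**Step 5. Smallest n meeting both targets exactly.** A search over n from 30 to 59, taking at each n the smallest cut-off with type I error at or below 0.10, first succeeds at n = 41 with a cut-off of 21: type I error 0.0965, power 0.9035. Because of discreteness, n = 42 (cut-off 22) falls back to 0.8775.

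**The case against.** The best defence concerns weight, not arithmetic. A test with attained size 0.074 is a valid level-0.10 test, and quoting the nominal level for a discrete test is ordinary practice; on that reading the alpha statement is a ceiling and is not wrong. The power gap is 3 points, and the rule reaches 90% power only 1.2 points above the planned alternative. No interim decision depends on power. The sample size, the cut-off, the estimate and its Clopper-Pearson interval are all unaffected. The 90% also looks like the output of a recognised formula, with the cut-off then set to protect alpha, which would be a mismatch of methods and not an unfounded number.

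Much of this stands. The alpha statement is acceptable as a nominal level, although quoting the attained 7.4% beside it would help. The consequence is modest, and the origin of the 90% is an inference because no method is named. Section 14.5.4 restates the rule correctly and needs no change.

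None of it rescues the power figure. The plan ties its primary decision to 21 of 40, 87.0% does not round to 90%, and the formula that yields 90% describes a test rejecting at 20, whose exact type I error is 13.0%.

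**Conclusion.** The power statement is wrong as written in Section 14.2 and in the synopsis. For the rule the plan will apply, exact power at a 60% rate is 87.0% against 90% stated, with exact one-sided type I error of 7.4% at 40%. The stated combination cannot be had with any integer cut-off at n = 40.

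The result rests on the plan's own inputs: exactly 40 evaluable subjects, independent binary outcomes with a common response rate, one look, and rejection at 21 or more. No outside figure is needed. The error slightly overstates the trial's ability to detect its target rate; it does not threaten the validity of a positive finding.

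**What to change.** In Section 14.2 and in the synopsis, replace the power sentence with wording such as:

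> With 40 evaluable subjects and rejection at 21 or more responders, the exact one-sided type I error is 7.4% at a true rate of 40% and the exact power is 87.0% at a true rate of 60%.

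The nominal one-sided 0.10 level can be kept beside it as the design ceiling. The change is one sentence in each of two places, and its only cost is a slightly lower stated power. Enrolment, cut-off, primary analysis and conduct are untouched.

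Restating the figures is sufficient. For information only, 41 evaluable subjects with the same cut-off of 21 would give type I error 9.65% and power 90.3%, should the sponsor wish to keep the 90% claim.

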14.3 Endpoint Definitions

14.3.1 Very Good Partial Response or Better

VGPR+ will be determined for each subject as a binary variable indicating whether or not the subject achieved a VGPR or better to induction, as determined by the IMWG 2016 response criteria (see Section 13.1).

14.3.2 Objective Response

Objective response will be determined for each subject as a binary variable indicating whether or not the subject achieved a best overall response of PR or better as determined by the IMWG 2016 response criteria.

14.3.3 Overall Survival

Overall survival (OS) is defined as the duration from enrollment to the study (treatment start date) to the date of death from any cause. Subjects who are alive or lost to follow-up at the time of the analysis will be censored at the last known date they were alive.

14.3.4 Progression Free Survival

Progression free survival (PFS) is defined as the duration of time from enrollment to the study (treatment start date) to first occurrence of either PD or death. Disease progression must be objectively determined per IMWG 2016 criteria (see Section 13.1), where the date of progression is the date of the last assessment that identified PD. If the subject died without documented disease progression, the date of progression will be the date of death. For surviving subjects who do not have documented disease progression, PFS will be censored at the date of last disease assessment. For subjects who receive subsequent anti-cancer therapy prior to documented disease progression, PFS will be censored at the date of last disease assessment prior to the commencement of subsequent therapy. Subjects who have an initial PFS event immediately following 2 or more consecutive missed disease assessments will be censored at the date of the last assessment prior to those missed assessments. For participants with only one missed assessment, the documented PD status and assessment date will be used.

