⁹ Serum chemistries: BUN, creatinine, (with calculated creatinine clearance at screening and on Day 1 of each cycle), glucose, uric acid, calcium, chloride, phosphorus, potassium, sodium, LDH, albumin, total protein, magnesium, total bilirubin, alkaline phosphatase, AST and ALT. **NOTE:** calcium should also be corrected for albumin.

¹⁰ CBCD: complete blood count with differential and platelets.

¹¹ If the screening serum B-HCG in FCBP is done within 24 hours prior to induction C1D1, it does not need to be repeated on C1D1. Pregnancy testing (serum or urine) must be repeated once a week (D1, 8, 15, 22) in induction cycle 1, and then monthly (D1 of each cycle) for subsequent cycles in FCBP.

¹² Tests to include: serum quantitative immunoglobulins (QIg; including IgA, IgM, IgG, IgD, IgE), serum protein electrophoresis (SPEP), urine protein electrophoresis (UPEP; 24-hr urine sample required), serum and urine immunofixation, and serum free light chain (FLC). If screening tests were performed within 14 days of induction C1D1, these do not need to be repeated C1D1 of induction. Testing for IgD and IgE will only be performed for subjects with IgD and IgE-type myeloma. Serum FLC to be performed on D1 of each cycle for subjects with light chain only disease and for subjects where a CR is suspected or maintained. After screening assessments, subjects without measurable urine M-Protein at

baseline will not be required to have UPEP or urine immunofixation repeated at subsequent disease assessment time-points, unless clinically indicated. Starting at maintenance cycle 14, disease evaluations should only be collected every 2 cycles (i.e., cycle 14, 16, 18, etc.)

¹³ Bone marrow aspirate and biopsy collected for disease assessment and correlative analyses at screening (pre-induction), post-induction (within 7 days prior to treatment on C1D1 of maintenance) and to confirm a CR. A bone marrow biopsy and aspirate will also be collected at relapse/progression for disease assessment and correlative studies at the discretion of the investigator. During maintenance, bone marrow biopsies and aspirates will be collected every 6 months (+/- 30 days) for disease evaluation per standard of care. See Section 8.8.3 for additional details. As of protocol Amendment 7 Version 8, research samples will no longer be collected on subjects on treatment or active follow-up for correlative analyses.

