8.2.2 Day 1 Cycles 1-4 (unless otherwise noted)

- **Physical Exam:** Symptom-directed physical exam (to include weight). Subjects should also be monitored for second primary malignancies. If a subject's weight changes by more than 10% from induction C1D1, the dose of carfilzomib and elotuzumab should be re-calculated. This re-calculated weight should be used as the new baseline weight. For office visits required during the COVID-19 pandemic, virtual visits will be allowed per investigator discretion starting with Cycle 2 Day 1 induction.
- **Performance Status:** ECOG performance status. For required time-points during the COVID-19 pandemic, performance status may be performed virtually if the office visit is being performed virtually (starting with Cycle 2 Day 1 induction)
- **Vital Signs:** Vital signs should include temperature, heart rate, blood pressure and respiratory rate. Measure prior to elotuzumab infusion.
- **Cardiac Evaluation:** ECG
- **Laboratory Assessments**
 - Serum chemistries: BUN, creatinine, (with calculated creatinine clearance on Day 1 of each cycle), glucose, uric acid, calcium, chloride, phosphorus, potassium, sodium, LDH, albumin, total protein, magnesium, total bilirubin, alkaline phosphatase, AST and ALT. **NOTE:** calcium should also be corrected for albumin.
 - CBCD: complete blood count with differential and platelets
 - Pregnancy test (serum or urine) in FCBP; **NOTE:** if screening pregnancy was done within 24 hours of C1D1 it does not to be repeated on C1D1.
- **Disease Evaluation:**
 - Blood and urine tests: Serum QIg (including IgA, IgM, IgG, IgD, IgE), SPEP, UPEP (24-hr urine sample required), serum and urine immunofixation, and serum FLC. Testing for IgD and IgE will only be performed for subjects with IgD and

IgE-type myeloma. Serum FLC to be performed for subjects with light chain only disease and for subjects where a CR is suspected or maintained. Subjects without measurable urine M-Protein at baseline will not be required to have UPEP or urine immunofixation repeated at subsequent disease assessment time-points, unless clinically indicated.

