8.7 Follow-up

For subjects who discontinue study treatment before relapse or PD, disease evaluations should continue to be performed until relapse or confirmed PD, death, start of a new anticancer treatment, withdrawal of consent to study participation, or until the criteria for the final analysis are met (Section 14.5.1) whichever occurs first. The schedule for disease evaluation should follow the schedule outlined during maintenance. Survival follow-up will occur every 3 months (+/- 30 days) from the last administration of protocol-directed therapy until death, lost to follow-up, or until the criteria for the final analysis are met (Section 14.5.1) and may be conducted via telephone. Any second primary malignancies discovered during long-term follow-up will be documented. Follow-up clinical information may also be obtained through chart reviews or other data sources (e.g. death registries).

The investigator is responsible for following the subject during the required follow-up period even if the subject lives elsewhere or has been released from his or her care and is being treated at another institution.

If the subject cannot be contacted following three attempted telephone calls over a period of 10 business days, the subject will be contacted in writing. Lost to follow-up is defined as four consecutive unsuccessful documented attempts (telephone and written) to contact the subject.

NOTE: in the event the criteria for the final analysis are met, and there are subjects who have not yet been discontinued from study treatment, subjects in follow-up will continue to be followed until all subjects have discontinued study treatment and completed the Safety Follow-up Visit (see above).

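### The PFS missed-assessment rule counts visits although the visit interval doubles at maintenance cycle 14, so equal gaps are treated differently, and it does not say whether deaths are exempt

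*Combined protocol and SAP*

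**What the plan says.** Section 14.3.4 measures PFS from treatment start "to first occurrence of either PD or death". For deaths it adds: "If the subject died without documented disease progression, the date of progression will be the date of death". Later in the same section comes the missed-assessment rule: "Subjects who have an initial PFS event immediately following 2 or more consecutive missed disease assessments will be censored at the date" (meaning the final test before the gap). The rule carries no limit in days or weeks. The sentence after it reads: "For participants with only one missed assessment, the documented PD status and assessment date will be used".

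The assessment schedule is set elsewhere. Sections 8.2.2 and 8.3.2 put disease evaluations on day 1 of each 28-day cycle in induction and maintenance. Footnote 12 of the Study Calendar (Section 7) then changes the spacing: "Starting at maintenance cycle 14, disease evaluations should only be collected every 2 cycles". Visit windows are ±2 days in induction (footnote 2) and ±14 days in maintenance (footnote 4).

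Section 14.3.6 gives DoR the same censoring as PFS. Section 14.3.5 does so for TTP, apart from deaths from other causes. Section 14.5.1 uses the PFS censoring rate (20%) as one of two triggers for the updated analyses.

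On survival, Section 8.7 says: "Survival follow-up will occur every 3 months". It allows contact by telephone and the use of death registries.

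**The concern.** A missed-assessment rule exists because a progression first seen after a long unobserved interval may have happened much earlier. What matters is the length of that interval. A rule that counts visits measures length consistently only if the spacing is constant, and here it doubles. The rule can therefore discard a progression that is fairly well located in time and keep one that is located less well.

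The reason for the rule does not extend to deaths, whose dates are known without any disease test. If deaths are caught, a subject too ill to attend two monthly visits who then dies is analysed as event-free at the last test. Such censoring is likely to be informative and would lengthen PFS and DoR.

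**Working it through.** The plan states no PFS sample size, event count or power, so there is no figure of its own to reproduce. The check builds the visit calendar and applies the rule to it.

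**Calendar.** Induction tests fall on days 0, 28, 56 and 84. Maintenance cycle 1 (M1) starts 28 days after induction cycle 4 starts (Section 5.2), on day 112. M14 falls on day 112 + 13 × 28 = 476, which is week 68 or about 15.6 months. After that the tests are M16, M18 and so on, 56 days apart.

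**Gap from last test to the visit showing PD.** The range is the nominal gap plus or minus the windows of the two attended visits.

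| Situation | Missed | Nominal gap | Range with windows | Rule |
|---|---|---|---|---|
| Within induction | 2 | 3 × 28 = 84 d | 84 ± (2+2) = 80–88 d | censored |
| Maintenance, up to M14 | 2 | 3 × 28 = 84 d | 84 ± (14+14) = 56–112 d | censored |
| M12 tested, M13 and M14 missed, PD at M16 | 2 | 28 + 28 + 56 = 112 d | 84–140 d | censored |
| M14 tested, M16 missed, PD at M18 | 1 | 2 × 56 = 112 d | 84–140 d | counted |
| From M14 | 2 | 3 × 56 = 168 d | 140–196 d | censored |

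The third and fourth rows have the same gap and opposite outcomes.

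**Deaths.** Take a maintenance test on day 0, with tests due on days 28 and 56 both missed. With the +14-day window the second test is not missed until day 70, and the next is due on day 84. A death on days 70–84 then directly follows two missed assessments. Read literally, it is censored at day 0.

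**Analysis trigger.** A 20% censoring rate in 40 subjects is 0.20 × 40 = 8 subjects. Each event turned into a censored observation permanently takes one of those eight places, so the 20% limb is reached later or not at all.

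**Illustrative size.** Assumptions: exponential PFS, a 36-month cut-off, and a share q of events before 15.6 months re-coded as censored 84 days earlier. The two medians are those cited for KRd in Section 1.2. The values of q are assumed.

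- Median 15.4 months: the share of events before 15.6 months is 1 − 2^(−15.64/15.4) = 0.505, or 20.2 of 40. With q = 5%, 10% or 20%, about 1.0, 2.0 or 4.0 events are lost. The Kaplan-Meier median becomes about 16, 16.8 or 18.2 months, and 12-month PFS rises from 58% to 60%, 61% or 64%.
- Median 26.3 months: the share is 1 − 2^(−15.64/26.3) = 0.338, or 13.5 of 40. About 0.7, 1.4 or 2.7 events are lost, and the median becomes about 27, 27.8 or 29.3 months.

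**The case against.** **Deaths.** One sentence dates PFS at death when no progression was documented, and the sentence paired with the missed-visit rule speaks only of PD. A reader could take that pair to govern PD and the earlier sentence to govern deaths. This stands. A reader might infer that the plan definitely discards deaths, but the documents support only an ambiguity: the literal wording includes deaths, because PFS events are defined to include them, and nothing exempts them.

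**Timing.** It is tempting to say that any death from day 60 onward, after tests due on days 28 and 56 were missed, is censored. In maintenance that fails, because the day-56 test can still be done until day 70. Likewise, 12 weeks against 16 weeks is a nominal contrast. With windows the early censored range (56–112 days) and the late counted range (84–140 days) overlap. The inconsistency remains, because the outcome still depends on the visit count and not on the gap.

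**Size.** The values of q have no source in the documents. On treatment, disease tests share day 1 of each cycle with dosing, so missing two usually means missing two treatment visits, and nothing shows that 20% is plausible. The calculation also re-codes events from time zero, yet at the 15.4-month median about 23% of the early events fall before day 84, when a scheduled PD visit cannot yet follow two missed tests. With 40 subjects and that median, the sample median itself would range over roughly 9–22 months, far wider than the shifts shown.

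**Consequence.** PFS, TTP and DoR are secondary and are estimated by Kaplan-Meier without a hypothesis test. This also stands and limits the importance of the point.

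**Conclusion.** The rule as written treats equal gaps unequally. This follows from Section 14.3.4 and calendar footnote 12 alone and needs no assumption about missed visits. Whether deaths are exempt is unclear, and two programmers could code the same death differently. Both faults reach PFS, DoR and the 20% trigger. TTP is reached through progression only.

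The direction, if it operates, is toward longer PFS and DoR. The size is unknown. Under the assumed 5–20%, it is about 1–4 lost events of 40 at a 15.4-month median, or about 0.7–2.7 at 26.3 months. A reader might infer from these figures that the reported PFS will be materially biased, but the documents give no missed-visit rate that would support that. The primary VGPR+ test is unaffected. The change is worth making because it is cheap and removes a coding ambiguity before analysis.

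**What to change.** - State in Section 14.3.4 that a death before new anti-cancer therapy is a PFS and DoR event on its date, whatever assessments were missed.
- Apply the missed-assessment rule to PD only, with one time limit for the whole study that allows for visit windows. For example, censor PD only if more than 140 days have passed since the last assessment: 2 × 56 + 14 + 14 = 140. With visits inside their windows, no late PD counted today then becomes censored. A limit of 112 days would not do this, because it equals the nominal late gap after a single missed visit. If both visits fall evenly over whole days in their windows, about 48% of those PDs would exceed it.
- Say what counts as missed, including partial test panels and visits outside the window.
- Report the present visit-count rule as a sensitivity analysis, stating how deaths are handled in it.

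The cost is SAP wording and one extra run, with no new visits, data or subjects. There are three downsides. PFS may come out slightly shorter. Some PD dates will carry up to 20 weeks of uncertainty, which the current rule already accepts after cycle 14. A death long after assessments stopped may stand in for an earlier unseen progression, and the sensitivity run will show how much that matters.
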